## **SECTION 1. ABSTRACT**

---

### **Study Aims**

The aims of this study are to utilize non-invasive airway oscillometry measure pulmonary function and changes in respiratory mechanics over time in term and preterm infants with and without lung disease. We propose 4 Specific Aims:

- Aim 1: To quantify differences in respiratory mechanics between term and preterm infants.
- Aim 2: To utilize oscillometry to predict risk of bronchopulmonary dysplasia (BPD) in preterm infants with respiratory distress syndrome (RDS).
- Aim 3: To identify change in lung function in common neonatal respiratory disease states (BPD, RDS, transient tachypnea of the newborn (TTN), and meconium aspiration syndrome (MAS)).
- Aim 4: To evaluate pulmonary response to chronic therapeutic interventions.

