### **3.2. SECONDARY HYPOTHESIS OR QUESTIONS (S) (IF APPLICABLE)**

- 1) Oscillometry can detect disease progression (e.g., BPD, RDS, TTN and MAS) and resolution in infants hospitalized in the UAB NICU.
- 2) Oscillometry can inform therapeutic response to common pulmonary interventions (e.g., systemic steroids, inhaled steroids, and diuretics) in infants hospitalized in the UAB NICU.
- 3) To determine how pulmonary function differs over time between preterm infants with RDS which resolves and preterm infants with RDS who go on to develop BPD.
- 4) To determine the effects on pulmonary function measurements of medications and treatments given to newborn infants to treat bronchopulmonary dysplasia including physical therapy, methylxanthines, furosemide, chlorothiazide, inhaled and systemic corticosteroids, cromolyn sodium, and albuterol.

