#### **4.1.1. Inclusion Criteria**

Infants must meet all of the following criteria to be eligible:

Infants  $\geq 22+0/7$  weeks' gestation at birth.

Infants whose parents/legal guardians have provided consent for enrollment.

Infants admitted to the regional neonatal intensive care unit (RNICU) or the newborn nursery (NBN) at UAB.

Off ventilator/CPAP support for  $\geq 12$  hours before study entry.

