#### **4.2.3. Study Intervention and Comparison**

Term and preterm infants with and without newborn lung disease will have serial oscillometry to evaluate neonatal lung function. Infants will have pulmonary function testing performed using the forced oscillation technique at baseline after enrollment in the study. This will be repeated after 24 hours, 48 hours and once per week thereafter among infants who remain hospitalized.

Infants with lung disease who are receiving pulmonary medications or treatments for lung disease, as per physician order, will have additional measurements of pulmonary function before and after these treatments are given.

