#### **4.2.4. Control or Monitoring of Co-interventions**

Aim 1 control: baseline oscillometry measurements will be compared over time between preterm infants and term infants without lung disease as defined by need for respiratory support.

Aim 2 control: preterm infants with RDS who go on to develop BPD will be compared with preterm infants with RDS who do not go on to develop BPD. Preterm infants who do not develop BPD will serve as controls for RDS infants who develop BPD.

Aim 3 control: baseline pulmonary function tests and serial changes over time will be compared between infants with and without lung disease. Preterm infants without lung disease will act as controls for preterm infants with lung disease. Term infants without lung disease will act as controls for term infants with lung disease.

Aim 4 control: The timing of pulmonary function testing among infants with lung disease will be recorded in relation to the timing of interventions, as ordered by the treating physician, which may affect pulmonary function including bronchodilators, steroids, diuretics, methylxanthines, different forms of physical therapy, and nebulized/inhaled medications, to determine the effects of these treatments on pulmonary function pairing the pre-treatment pulmonary function values (control) for an individual patient with the post-treatment values (intervention) for the same individual patient.

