#### **4.2.5. Primary Outcome**

The primary outcome will be change in lung reactance at 7 Hz ( $X_7$ ) quantified by oscillometry in each comparison group.

In Aim 1, we will compare lung function between term and preterm infants without lung disease at baseline, 24 hours, 48 hours, 72 hours, 7 days, and weekly thereafter until discharge.

In Aim 2, we will compare lung function between preterm infants with RDS who develop BPD and those who do not develop BPD.

In Aim 3, we will longitudinally evaluate change in lung function in NICU patients with lung disease (BPD, RDS, TTN, MAS) at diagnosis, 24 hours, 48 hours, 72 hours, 7 days, and weekly thereafter until resolution of disease state or NICU discharge.

In Aim 4, we will longitudinally evaluate lung function response to therapeutic intervention.

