### 5.1. STATISTICAL ANALYSIS PLAN

Results will be analyzed by the Student's t test, as appropriate for parametric data, and by Mann-Whitney U rank sum test for nonparametric data. A  $p$  value of  $<0.05$  will be considered statistically significant.

Non-independent parametric data will be analyzed by the paired Student's t test, and Wilcoxon signed rank test for non-independent non-parametric data.

Chi-square or Fisher's exact test will be used as appropriate to analyze categorical data.

Analysis of covariance and multiple regression models will be used to examine the interaction between, and the independent effects of factors including birth weight, gestational age, gender, ethnicity, socioeconomic group, maternal smoking, type and severity of lung disease, treatment with surfactant (including number of doses), days of mechanical ventilation before study entry, days of respiratory support before study entry, treatment with antenatal steroids, and treatment with postnatal steroids upon primary and secondary outcomes.

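### Aim 2 is worded as predicting BPD, but the plan only compares lung function by later BPD status and specifies no analysis of predictive performance

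*Combined protocol and SAP*

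**What the plan says.** **The aim.** The abstract (Study Aims) gives Aim 2 as: "To utilize oscillometry to predict risk of bronchopulmonary dysplasia (BPD) in preterm infants with respiratory distress syndrome (RDS".

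**The planned comparison.**
- The abstract (Study Design Type) lists BPD against non-BPD among the cross-sectional comparisons.
- Section 3.2, item 3, asks "how pulmonary function differs over time between preterm infants with RDS which resolves" and those whose RDS is followed by BPD.
- Section 4.2.4 says that infants with RDS who later develop BPD "will be compared with preterm infants with RDS who do not go on to develop BPD".
- Section 4.2.5 says: "In Aim 2, we will compare lung function between preterm infants with RDS who develop BPD and those who do not develop BPD".
- Section 5.2 (Aim 2) sizes the study for a 20% difference in initial X7 between these groups, 132 in each.

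**The analysis.** Section 5.1 lists t, Mann-Whitney, paired and categorical tests, then analysis of covariance and multiple regression. The regression factors include birth weight, gestational age, and the kind and severity of lung disease. The list ends with "treatment with postnatal steroids upon primary and secondary outcomes", so the dependent variables are the lung measures.

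**The timing.** Section 4.1.1 makes it an entry condition to be "Off ventilator/CPAP support for" at least 12 hours. Section 4.2.3 says: "Infants will have pulmonary function testing performed using the forced oscillation technique at baseline after enrollment in the study". Section 5.2 counts an oxygen requirement at 28 days as (mild) BPD. No section sets a maximum postnatal age at entry or at first test.

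**The concern.** Prediction and group comparison are different questions. A comparison of means asks whether X7 differs on average between infants who later have BPD and those who do not. Prediction asks how well an infant's X7 separates the two outcomes, and whether the resulting risks are accurate. With a few hundred infants, a difference in means can be clearly significant while the two distributions overlap heavily.

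As written, the Aim 2 result would be a p value for a difference in X7, while the aim's wording invites reporting it as prediction. The plan commits to no AUC, threshold, sensitivity, specificity or calibration. If these are added after the data are seen, the model, time window and cut-off become post hoc choices, in a study that describes its aims and hypotheses as specified in advance.

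Timing matters for the same reason. An X7 measured after an infant has met the 28-day criterion describes disease that is already there and cannot count as a predictor of it.

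**Working it through.** **1. Reproduce the plan's figure.** Inputs from section 5.2 (Aim 2): difference 0.20 and SD 0.50, both as fractions of the mean; power 90%; type I error 5%. Two-sided testing is assumed, since section 5.2 does not state it.

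- d = 0.20 / 0.50 = 0.4
- n per group = 2(1.960 + 1.282)² / 0.4² = 131.3, rounded up to 132; total 264
- Power at 132 per group by the noncentral t distribution: 89.9%
- A one-sided test would need 108 per group, so the stated figure is the two-sided one

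The 264 reproduces. It is the sample size for a difference between two means.

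**2. What that effect means for discrimination.** Assume X7 is normal with equal variance in the two groups.

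- AUC = Φ(d/√2) = Φ(0.283) = 0.611
- Hanley-McNeil standard error at 132/132: A(1−A) = 0.2376; Q1 = A/(2−A) = 0.4402; Q2 = 2A²/(1+A) = 0.4639; A² = 0.3738. SE = √{[0.2376 + 131(0.4402 − 0.3738) + 131(0.4639 − 0.3738)] / 132²} = 0.0345
- 95% CI: 0.611 ± 1.96 × 0.0345 = 0.544 to 0.679
- Sensitivity at 80% specificity: 1 − Φ(0.842 − 0.4) = 33%

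The effect for which the study has 90% power is thus compatible with weak discrimination. This re-expresses the planning assumption; it is not an estimate for X7.

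**3. What section 5.1 can and cannot give.** If BPD status is entered as the disease term, the planned covariance analysis gives the BPD/non-BPD difference in X7 adjusted for gestational age and birth weight. Section 5.1 does not say that BPD status will be that term for Aim 2. Even so, the model runs from clinical factors to X7. It yields no risk of BPD for an infant, no AUC and no calibration.

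**4. Timing.** Entry waits for at least 12 hours off support, the first test follows enrolment, and no upper age is set. An infant supported past day 28 could therefore have a first X7 after meeting the 28-day criterion. The documents give no basis for counting such infants.

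**The case against.** The strongest reply is that the regression in section 5.1 already addresses added information. This largely stands. A reader might infer that the plan gives no estimate of whether X7 carries information beyond gestational age and birth weight, or that it could not tell an informative X7 from a redundant one. The documents do not support that, provided BPD status is the disease term. Simulations at 132 per group (1,000 runs per scenario) assumed a clinical score with AUC 0.70 or 0.80 and a within-group correlation with X7 of 0 or 0.3. The covariance group term and a logistic X7 term reached the same significance verdict in 98 to 99% of runs. Power of the covariance and logistic terms was 87% and 86% (AUC 0.70, correlation 0), 33% and 33% (0.70, 0.3), 78% and 77% (0.80, 0), and 6% and 6% (0.80, 0.3). What is missing is the measurement of predictive performance.

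Second, section 5.2 speaks of initial measurements in infants who develop BPD afterwards, and says this status cannot be known in advance. Section 4.2.2 has parents approached on admission, and Aim 3 has its own BPD comparison. The intent to test first is clear, and an infant who already meets the criterion does not fit the Aim 2 description. But no stated rule enforces this, and early consent does not remove the off-support condition.

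A reader might also infer that every first test after day 28 describes BPD already present. That is wrong: with no upper age, an infant without BPD can also be first tested late.

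Third, only the Study Aims use the word predict for Aim 2, so the mismatch might be called one of wording. That is a fair reason to offer rewording as a complete remedy.

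**Conclusion.** The point holds in this form: Aim 2 promises prediction, and the plan specifies a comparison by later BPD status with no measure of how well X7 predicts BPD. A significant result would show association, possibly adjusted for gestational age and birth weight, and would not by itself support a prediction claim. The size is illustrated by the AUC of about 0.61 (95% CI 0.54 to 0.68) at the powered effect, which rests on the plan's d = 0.4 and on equal-variance normality.

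The timing gap is real but secondary. Its frequency, and the size and direction of any effect on the results, cannot be judged from the documents, so it should not be described as demonstrated bias. Nor is the Aim 2 sample size in error; it is correct for the comparison it describes. The mismatch should be resolved before analysis.

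**What to change.** Choose one of two routes.

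**(a) Reword.** State Aim 2 in the Study Aims as an association aim, in line with section 3.2, item 3, and do not report its result as prediction. This is a wording edit; the cost is giving up the prediction claim.

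**(b) Keep the prediction aim and add its analysis to section 5.1.**
- Fit a logistic regression of BPD on the first X7 obtained before day 28, with gestational age, birth weight and age at test.
- Report the AUC with and without X7, with bootstrap optimism correction and 95% CIs, plus calibration. Present these as estimates, not as a powered test.
- Count infants of either group with no test before day 28, leave them out of this analysis, and limit the claim to infants tested before day 28.
- Keep the comparison of means in section 5.2 as the powered association analysis.

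Route (b) needs SAP text and modelling of data already to be collected. Its cost is a narrower claim and fewer infants. The share without an early test is not given, so 10% to 50% is assumed. Power of a comparison of means limited to early-tested infants, from 89.9% at 132/132 (d = 0.4, noncentral t), would be:

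| Infants lost | BPD / non-BPD at 10% | Power | BPD / non-BPD at 50% | Power |
|---|---|---|---|---|
| BPD group only | 119 / 132 | 88% | 66 / 132 | 75% |
| Both groups, not replaced | 119 / 119 | 87% | 66 / 66 | 63% |

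Keeping 132 early-tested BPD infants would need 132/0.9 = 147 to 132/0.5 = 264 infants with BPD. Section 5.2 allows open-ended RDS enrolment, which could offset part of the loss: 66 BPD infants with 198 or 264 non-BPD infants give 80% or 83%.

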### **Eligibility Criteria**

Infants in the UAB NICU or well-baby nursery will be eligible for enrollment. NICU participants must be off ventilator/CPAP support for  $\geq 12$  hours to be included in this study. Term and preterm infants without lung disease will provide comparative normative data on respiratory mechanics during the neonatal period. Disease cohorts will include BPD, RDS, TTN, and MAS as common respiratory disease represented in a NICU population. Clinical benefit of physician-directed treatments will assess response to systemic steroids, inhaled steroids, and diuretics.

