#### **Aim 2 (Comparison of BPD and non-BPD lung compliance)**

Assuming lung reactance at 7 Hz ( $X_7$ ) initial measurements will have an absolute 20% difference (more negative initially) in preterm infants with RDS who go on to develop BPD (including O2 requirement at 28 days –mild BPD) compared to preterm controls with RDS who do not develop BPD will need to recruit 264 infants (132 BPD, 132 non-BPD) assuming power of 90%, type I error rate of 5% and standard deviation of 0.5 of the mean.

It will not be possible to know in advance which infants with RDS will go on to develop BPD so we plan to enroll as many preterm infants with RDS as possible until the sample size for infants with RDS who develop BPD is reached.

Aim 2 (

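### Aim 2 is stated for all preterm infants with RDS, but an infant on ventilator or CPAP without a break to day 28 has no X7 before BPD, and no age limit keeps its later test out of the BPD group

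*Combined protocol and SAP*

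**What the plan says.** The abstract (Study Aims) gives Aim 2 as "To utilize oscillometry to predict risk of bronchopulmonary dysplasia (BPD) in preterm infants with respiratory distress syndrome (RDS"). Section 3.2 item 3, the Aim 2 control in section 4.2.4 and the Aim 2 outcome in section 4.2.5 name the same population. Section 4.2.4, for example, reads "preterm infants with RDS who go on to develop BPD will be compared with preterm infants with RDS" who do not. None of these places limits the aim by respiratory support.

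Entry is limited. The abstract (Eligibility Criteria) says "NICU participants must be off ventilator/CPAP support for" at least 12 hours. Section 4.1.1 repeats this as a criterion that every infant must meet ("Off ventilator/CPAP support for" at least 12 hours before study entry). Section 4.2.3 places the first test "at baseline after enrollment in the study". No exception is made for Aim 2, and testing on support is not described.

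Section 5.2 (Aim 2) assumes that "initial measurements will have an absolute 20% difference (more negative initially) in preterm infants with RDS who go on to develop BPD", and counts as BPD an oxygen "requirement at 28 days –mild BPD". It defines no other grade or time point. It plans 132 infants with BPD and 132 without, and enrolls infants with RDS until the BPD number is reached. No section sets a latest age for the initial measurement.

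**The concern.** A prediction needs a measurement taken before the outcome. For infants supported continuously to day 28, the entry rule and the 28-day definition together rule this out, yet the stated aim includes them. Two things are at stake.

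- **Scope.** A positive result would be reported as prediction of BPD in preterm infants with RDS, although it rests only on those who came off support before day 28.
- **Timing.** An infant that enters after day 28 has a first test that describes BPD already present. As written, that test can serve as its initial X7 in the BPD group, so the comparison would mix prediction with description of existing disease.

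**Working it through.** **1. The plan's own figure.** Inputs from section 5.2 (Aim 2): difference 0.20 and SD 0.50 (both as fractions of the mean), type I error 5%, power 90%, equal groups. Sidedness is not stated.

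n per group = 2 × (1.960 + 1.282)² × (0.50 / 0.20)² = 2 × 10.51 × 6.25 = 131.4, rounded up to 132, or 264 in total.

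This reproduces the plan with a two-sided test; power at 132 per group is 90.1%. A one-sided 5% test would give 108 per group and does not reproduce it. The arithmetic is sound. The question is which infants it describes.

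**2. Timeline of one infant.** I read 28 days as postnatal age. Take a preterm infant with RDS, on ventilator or CPAP with no 12-hour break through day 28, and needing oxygen on that day.

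- Before day 28: not eligible (section 4.1.1), so not enrolled and not tested (section 4.2.3).
- Day 28: has BPD by the section 5.2 definition.
- After 12 hours off support, later: eligible, and has a first test.

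No X7 exists from the time when BPD was still to be predicted. The only initial X7 follows BPD, and no rule in section 4.2.3, 4.2.5 or 5.2 keeps it out of the Aim 2 comparison.

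**3. What adjustment can do.** Section 5.1 lists days of ventilation and days of respiratory support before study entry as covariates. These can adjust among infants with a measurement. They cannot supply a pre-BPD measurement that was never made, and they do not change what a test after day 28 measures.

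**4. Size.** The documents do not say what share of infants with RDS and BPD can be tested before day 28. If that share is t, the number of infants with BPD needed to yield 132 predictive cases is 132 / t:

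| t (assumed) | Infants with BPD needed |
|---|---|
| 1.0 | 132 |
| 0.8 | 165 |
| 0.6 | 220 |
| 0.5 | 264 |
| 0.4 | 330 |

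These values illustrate the effect on recruitment. They are not estimates.

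**The case against.** The strongest reply is that eligibility criteria define the population and an aim need not repeat them. The off-support rule stands in the same abstract as Aim 2, and an initial measurement can exist only in an enrolled infant, so the 20% may already refer to testable infants. The exclusion is also partial: one 12-hour break before day 28 is enough, infants off support but still on oxygen can enter, and a return to support after entry does not remove the earlier test.

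Most of this stands. It does not meet the two gaps that remain: the plan never says that its entry rule takes some future BPD infants out of the prediction question, and it does not stop their later tests from being counted.

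A reader might infer more, namely that the missing infants are the most severe, that the true difference is therefore below 20%, and that Aim 2 is underpowered. The documents do not support this.

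- They give no severity data. That infants who come off support earlier have milder BPD is an inference from length of support.
- A smaller difference follows only if support to day 28 tracks the severity that drives both BPD and X7. Suppose half of BPD infants are untestable and BPD affects 30 to 50% of infants with RDS. A simulation with perfect tracking, starting from 20%, gives a difference of about 14 to 15%. With a correlation of 0.5 it gives about 18 to 19%. With zero correlation it stays at 20%.
- Power at 132 against 132 is the wrong quantity, because enrollment continues until 132 BPD cases are reached. In the same setting the BPD share among testable infants is 0.25 / 0.75 (BPD share 50%) or 0.15 / 0.85 (30%). Enrollment is then 396 or 748, with 264 or 616 infants without BPD. Power is about 75 to 89% with perfect tracking, 92 to 97% with a correlation of 0.5, and not reduced with none.

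**Conclusion.** The concern holds as a mismatch between the stated population and the infants who can give a predictive measurement, together with a missing time limit on that measurement. It follows from the protocol's own text and rests on one reading, that 28 days means postnatal age. Following the plan as written could give a conclusion that is too broad and, where first tests fall after day 28, partly not predictive.

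How many infants are affected cannot be worked out from the documents. They also do not show that the difference in testable infants is below 20% or that power is below 90%, so neither is claimed. The sample size of 264 is correct for its stated inputs.

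**What to change.** - **Aim and conclusion.** In the abstract, section 3.2 item 3, section 4.2.4 and section 5.2, restate Aim 2 as applying to preterm infants with RDS who are off ventilator and CPAP for at least 12 hours before day 28, and limit the conclusion to them.
- **Measurement window.** In the Aim 2 comparison, use only initial X7 measurements taken before day 28, in both groups. Later first tests can still serve the description of BPD in Aim 3.
- **Assumption.** State in section 5.2 that the 20% difference is assumed for this testable group. No new power figure is needed.
- **Reporting.** From the screening log (section 4.2.1), report how many infants with RDS reached day 28 without becoming testable. Give their BPD status only where it is available without added consent. The log is described as listing potentially eligible patients and is not said to record length of support or oxygen at day 28, so the count may need a field added.

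Eligibility, care and the testing schedule do not change. The cost is a narrower claim and fewer countable BPD cases, so reaching 132 may take longer than the two years planned in section 5.4, by an amount that the documents do not allow one to estimate.
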